We will collect data from four primary sources: the VA CPRS, RA observations, a RA-administered 10-minute patient survey, and brief qualitative follow-up interviews with patients, nurses, and physicians. A fifth source will be follow-up phone calls to identify three-day and 30-day ED revisits that have occurred outside of the VA healthcare system. Survey data will be electronically linked to CPRS data using a subject-level linking code stored separate from these data. Brief qualitative interviews will be audio recorded, transcribed without identifiers, and electronically linked to survey data. The RA will enter de-identified survey data from each in-person survey (using tablets) into a VA security-compliant electronic REDCap database hosted by VA Informatics Computing Infrastructure (VINCI). VINCI will build a virtual environment to house all study data as well as the necessary statistical tools for data analysis. We will capture data from qualitative interviews by notes and audio recordings that will be transcribed for analysis.

Follow-up interviews with intervention Veterans who are willing to speak more extensively after discharge from their ED visit will be used to obtain a more detailed understanding of patients' ED experience of barriers and facilitators of HAD use and anticipated future use of a hearing device in medical and other settings. Brief semi-structured interviews with ED nurses and physicians (providers) around the time of patient discharge will be used to assess providers' experiences interacting with hearing-impaired patients with and without HADs to evaluate, from the provider's view, the benefits and feasibility of use of the PockeTalker™ in the ED. Although almost all providers in the Harbor ED system are primary English speakers, we will also inquire as to provider dominant language at each encounter until we have a complete provider inventory for dominant language. We will use an explanatory sequential mixed methods design to develop semi-structured interviews for nurses and physicians in order to address additional areas of inquiry raised by the quantitative findings and/or discrepancies between qualitative and

quantitative data collected during the ED visit. Patient and provider interviews will be audio recorded, transcribed, and coded for themes.

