With regard to semi-structured interviews with staff (nurses and physicians), all staff will be informed about the study procedures in terms of 1) knowing that this is a study about hearing impairment; 2) that we are interested in understanding the utility of using HADs during an ED visit and that we will match staff characteristics (gender and spoken language) with each patient that is an enrolled subject. Staff will also know that a research assistant may approach them for a brief conversation about their experience with specific patients and about HAD use, in general. They will understand that they are free to participate or refuse participation and their decision will not be known to their supervisor and will not impact their employment in any way. They will be asked permission for the RA to audio record their conversation and they will know that as soon as that conversation is transcribed (and without identifiers), that tape recording will be erased. They will also know that we will attempt to survey all nurses and physicians at least once who are working during those times that patients are participating in HearVA-ED.

Methods for Dealing with Data Transformations

Missing – Missing data will be removed by multiple imputation or by being re-coded into a “missing” category.

Distribution of Data – The distribution of the data will be determined. Non-normally distributed data will be transformed using log transformation.

Definitions of Analytical Sets

Intent-to-treat – Analysis will be conducted with patients included in their randomly assigned group (opt in versus opt out), regardless of the treatment received.

Complete-case – Analysis conducted including only participants who have no incomplete data regarding their treatment.

Adverse and Serious Adverse Events

Standard IRB-approved and HIPAA compliant measures will be used to maintain Veteran confidentiality, privacy, and data security that adhere to the standards of the VA privacy officer, Information Security Officer, and Chief Information Officer. All study personnel have already taken or will take the mandatory VA HIPAA training to ensure that they are aware of the importance of Veteran confidentiality and all appropriate laws regarding the protection against Veteran privacy breaches. Procedures will be in place to ensure that all files containing Veteran information will be kept in VA-encrypted, locked databases on VA computers. There will also be

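### The SAP does not place research contact with providers after discharge instructions and the patient's survey, leaving an avoidable, probably modest, route for contamination of the control arm

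*SAP*

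**What the plan says.** **Who treats whom.** SAP, Method of randomization: individual patients are randomised after consent, stratified by site. No staff member is assigned to one arm. The section expects the arms to differ in nothing but whether a device was given.

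**What staff are told.** SAP, Definitions of Covariates (paragraph on staff interviews): all staff are informed of the study, including "knowing that this is a study about hearing impairment". They are also told that "we will match staff characteristics (gender and spoken language) with each patient that is an enrolled subject" and that "a research assistant may approach them for a brief conversation about their experience with specific patients and about HAD use, in general".

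**When staff are contacted.** SAP, Specific description of how data will be collected, describes two contacts:
- On language: "we will also inquire as to provider dominant language at each encounter until we have a complete provider inventory for dominant language".
- On experience: "Brief semi-structured interviews with ED nurses and physicians (providers) around the time of patient discharge", covering experience of "interacting with hearing-impaired patients with and without HADs". Controls are therefore included.

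**How many staff.** The Protocol's Study Outline plans 10 interviews with nurses and physicians. The SAP says "we will attempt to survey all nurses and physicians at least once", limited to those on duty while patients are taking part.

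**When outcomes are measured.** The patient survey follows ED care (SAP, Method of randomization). It covers hearing and understanding in the ED, preparation for going home, and accuracy of understanding of the discharge instructions (SAP, Definitions of Covariates). Neither document fixes the order of provider contact, discharge instructions and survey.

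**The concern.** Eligibility requires a score above the HHIE-S cut point. A provider who is asked about an enrolled patient without a device can infer that this patient screened positive and is a control. If the discharge instructions are still to come, the provider may speak up, repeat points or write them down. HAD patients are already visible by their device, so the new information falls mainly on controls.

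Two of the surveyed outcomes, preparation for discharge and understanding of the instructions, are formed at just this moment. Better communication with some controls would shrink the arm difference on them. The documents do not name the primary outcomes behind Goal 3. I take it that these survey measures are among them. If so, the first effect estimate, and the evidence for decision makers under Goal 4, would understate what the device adds to usual care by this route.

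**Working it through.** **1. The plan's own figure.** The SAP's enrolment steps reproduce:
- 1800 × (0.35 × 0.33 + 0.65 × 0.02) = 231.3 (stated 230)
- 230 × 0.70 = 161 (stated 160)
- 160 × 0.50 = 80
- 80 × 0.95 = 76
- 76 × 0.90 = 68.4 (stated 68)

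This supplies N = 68 and says nothing about contamination. The documents give no contamination rate, effect size or SD.

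**2. Model.** Let f be the fraction of controls whose provider is alerted before giving discharge instructions, and k the share of the HAD benefit that an alert reproduces. With true difference δ, the observed difference is δ − f·k·δ = δ(1 − f·k). A later trial sized on the diluted estimate grows by 1/(1 − f·k)².

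**3. Exposure f.** From the documents: 10 provider interviews (Protocol) and N = 68. Assumed: 1:1 allocation, hence 34 controls; one interview per patient; every such interview precedes the instructions. The last assumption makes f an upper figure for the stated number of interviews.
- Half the interviews concern controls: f = 5/34 = 0.147
- All concern controls: f = 10/34 = 0.294

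**4. Dilution.** k is assumed throughout. The last row is an illustration, since the SAP's aim of reaching all staff on duty does not fix f.

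| f | Dilution, k = 0.25 | Dilution, k = 0.5 | Later-trial inflation, k = 0.5 |
|---|---|---|---|
| 5/34 | 3.7% | 7.4% | 1.17 |
| 10/34 | 7.4% | 14.7% | 1.37 |
| 0.5 (illustration) | 12.5% | 25% | 1.78 |

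With 10 interviews and a larger trial, dilution is smaller. At N = 120 and k = 0.5 it is 0.5 × 5/60 = 4.2% to 0.5 × 10/60 = 8.3%.

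**5. Would the pilot show it?** For a standardised difference at N = 68, the 95% half-width is about 1.96 × √(2/34) = 0.48 SD. For an assumed δ of 0.5 SD, dilution of 7.4% to 14.7% is 0.5 × 0.074 = 0.04 SD to 0.5 × 0.147 = 0.07 SD. The pilot could not detect this. Sampling error is much larger, but the dilution is systematic and would stay in the estimate.

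**The case against.** There are five fair points on the other side.

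- **The language question is not about the patient.** It asks for the provider's own language and stops once the inventory is complete. The encounter may even be the interview itself, since the sentence follows the one on interviews. A reader might infer that research staff discuss identifiable patients with providers at every encounter. The text does not support that. What stands is narrower: staff are told their language and gender will be matched to each enrolled patient, so a question put during care can still mark that patient.
- **The interviews look retrospective.** They ask about experience, which presupposes that the interaction has taken place, and the approach about specific patients is optional. This stands for most communication during the visit. It does not settle discharge teaching, because contact near discharge may fall on either side of it.
- **Few interviews are planned.** On the Protocol's count of 10, exposure is limited, and the SAP's wider aim is a target per provider, not per patient. This stands and keeps the likely size modest.
- **The direction is not certain.** Arms are visible and most survey outcomes are self-reported, so expectation could favour the HAD arm. A reader might infer that the trial will understate the effect. The documents support only that this one pathway pushes toward zero.
- **The remedy is partial.** Staff will still know the study's subject, and a provider interviewed about one patient may treat later patients differently. This stands too.

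**Conclusion.** The concern holds in a limited form. The plan leaves the order of provider contact, discharge instructions and patient survey open, and contact that comes first can alter how a control patient is prepared for discharge.

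On the Protocol's 10 interviews, the plausible dilution is about 7% to 15%. This rests on N = 68, 1:1 allocation, contact before instructions in every case, and k = 0.5. It is lower if interviews mostly follow the instructions or if k is smaller. It is higher if surveying all staff exposes more controls.

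A reader might go further and conclude that a later trial would be planned about 1.8 times too large. That needs half of all controls to be alerted with k = 0.5, and nothing in the documents establishes such exposure. The net bias, with all open-label effects counted, cannot be signed from the documents. The case for acting rests on the low cost of closing an avoidable route, not on a demonstrated large effect.

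**What to change.** Make two wording changes in the SAP and the study procedures:

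1. Replace the language question at encounters with a one-off inventory of staff language and gender, completed during the four-month start-up and updated for new staff away from patient care. The plan already intends an inventory, so this changes mainly when and where it is taken.
2. In place of interviews near discharge, state that any provider conversation about a specific patient, in either arm, takes place only after that patient has received discharge instructions and completed the post-ED survey.

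**Cost.** Some providers will have gone off shift and will be interviewed later, with slightly poorer recall. No added staff, patients or procedures are needed. The change does not remove general staff awareness of the study, and reports of the effect estimate should say so.

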completion, 68 Veterans per year will complete this study. These highly conservative estimates ensure that we will achieve our desired minimum sample size of 180 Veterans if we continue the study beyond one year of recruitment. Our minimum goal for 12 months is 68 Veterans and maximum goal is 120.

We used simulation methods to estimate power and sample size requirements. We generated data from literature-based assumptions in each iteration for a specific sample size and an assumed effect size for each outcome. For each iteration, we conducted two t-tests in accordance with the multiple testing corrections and recorded whether one or both null hypotheses were rejected. For each sample size/effect size combination, we ran 1500 iterations; we calculated power as the proportion of iterations in which both null hypotheses were rejected. We evaluated total study (both arms) sample sizes ranging from 70 to 150.

We used simulation methods to estimate power and sample size requirements. We generated data from literature-based assumptions in each iteration for a specific sample size and an assumed effect size for each outcome. For each iteration, we conducted two t-tests in accordance with the multiple testing corrections and recorded whether one or both null hypotheses were rejected. Note that sample size estimates will only be relevant should be given approval to continue for the four-year duration of the Merit. Given the nature of this "developmental" Merit, continuation beyond 18 months is contingent on our findings at that time.

Specific description of how data will be collected

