We will use Grounded Theory, a systematic and rigorous set of principles for text interpretation developed by Strauss and Corbin to interpret qualitative data from semi-structured interviews. Audio-recorded qualitative data will be transcribed verbatim. [name] and a research assistant will analyze the data using an inductive thematic text analysis approach, involving a rigorous review of the transcripts to identify key concepts and patterns. We will use ATLAS, a qualitative data analysis management software program to facilitate our multi-step iterative coding and analysis. Initially, meaningful statements that convey discrete concepts and ideas will be identified and allocated a code that maintains the meaning of the original expression as closely as possible. The coders will independently read and analyze a sample of interview transcripts to identify preliminary codes and sub-themes. The constant comparative method of analysis will be used to continually refine the interview and coding procedure. This method involves an iterative process of making comparisons at each level of analysis (data with data, data with codes, codes with categories, etc.) throughout data collection and analysis. This process allows investigators to continuously modify and refine coding and create categories as data is being collected and analyzed. After the initial round of coding, we will recode all interviews to ensure that the final codes are applied equally to all interviews. We will develop a coding manual using this iterative process. All transcripts will then be independently coded by the two reviewers to establish inter-rater reliability. We will group the codes into higher-level categories to be distilled into the main research themes. Over the course of the process, we will maintain a record of the process of idea generation, analyses, questions, and hypothesized understandings. In the final analysis stage, will integrate qualitative and quantitative data to describe the mechanism of HAD effectiveness.

Method of randomization

After consent, we will randomize subjects to receipt of a HAD or control. Randomization will be stratified by site to ensure a balance of intervention and control subjects at each site. The RA will provide subjects given HADs with instructions and will fit and test the devices to ensure

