proper function. These subjects will be encouraged to use the HAD during any encounters with ED staff and others (for example, family). All consenting subjects will understand that consent includes: (1) completion of a post ED-care 10- minute survey and brief telephone follow-up four days after discharge, (2) abstraction of their medical records, and (3) awareness of the risks and benefits of participation. All consenting subjects will receive \$20 cash and be able to keep the HAD when leaving the ED if they have found it to be helpful. If randomization is successful, the two groups should vary only in receipt of the HAD, which we hypothesize will affect downstream outcomes.

Plan for and specification of the purpose of any interim analysis of the data

Before addressing the specific aims, the data will be summarized numerically using descriptive statistics. Comparison of the baseline characteristics between the two treatment groups will be performed using chi-square tests for categorical data and t-tests or nonparametric tests for ordinal or continuous data.

We will compare intervention and control subjects with respect to baseline sociodemographic characteristics (age, gender, race, and education), comorbid medical conditions, and the Charlson comorbidity index and other potential co-variable measures. We will assess whether any adjustments need to be made in the final statistical models if we determine the differences are clinically meaningful. Besides the primary analyses described below, we will conduct exploratory mediation analyses with the goal of developing a better understanding of the mechanisms of the intervention. We will use R 3.3.2 (R Foundation for Statistical Computing, Vienna, Austria) for all analyses.

Methods for handling missing data points and subject dropouts

Missing data: We anticipate less than 5% loss to follow-up, as a majority of data is collected during one ED visit. If missingness is higher, multiple imputation will be used to estimate the group differences and the uncertainty due to missingness, under the assumption of missingness at random (MAR).

Definitions of Covariates

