a system in place for breaches in Veteran privacy or other adverse events to be reported to the Principal Investigator, so that he may take the appropriate steps to ensure that they are documented and there is minimal risk that it could happen again. We will obtain approvals from the VA New York Harbor Healthcare System human subjects committee. Adverse events will be reported to the study IRB and will include any medical event regardless of its relationship to the study intervention.

SAE/EA Response and Reporting Procedure

1. Research staff become aware of AE/SAE (via scheduled survey, spontaneous report from participant, or other means)
2. Research staff notify PI immediately if the event is an SAE or if immediate psychiatric or medical intervention is required, and within 7 days if the event is an AE.
3. PI makes determination for 3 key indices if suspected to be study related:
 - a. Severity: Mild, Moderate, Severe
 - b. Expectedness: Expected, Unexpected
 - c. Study Related: Definitely, Probably, Possibly, Remotely, Not Study-Related
4. Project Director documents SAE/AE and PI determination in study database.
5. Project Director prepares a report for the local IRB as per local, state, and federal reporting requirements.
6. PI and Project Director plan measures to prevent future occurrences, if any warranted.
7. PI and Project Director make changes to protocol and/or consent form if needed

Data and Safety Monitoring Plan

As this is a minimal risk, single site study, – (Brooklyn and Manhattan campuses are both part of VANYHHS). A DSMB is not required.

Data and Safety Monitoring Plan (DSMP): Our study team will monitor all adverse events through weekly meetings to review enrollment progress and identify any adverse events. We will evaluate any adverse events related to recruitment, enrollment, hearing assistance device use, and the interview process. Adverse events will be reported to the study IRB and will include any medical event regardless of its relationship to the study intervention. All such events will be recorded and blinded (where possible) except for the IRB, who will be unblinded and notified immediately of any serious and unexpected event. In such instances, the IRB will determine appropriate action with respect to reporting and additional steps. For more urgent situations, the study interviewer will notify ED staff and any of the physician investigators on the team.

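### Randomisation is stratified by site, but no described analysis includes site and the adjustment rules are unlikely to add it

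*SAP*

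**What the plan says.** - **Design.** SAP, Method of randomization: "Randomization will be stratified by site to ensure a balance of intervention and control subjects at each site". Site is the only stratification factor. Block size and the way the sequence is generated are not given. There are two campuses (SAP, Data and Safety Monitoring Plan: "Brooklyn and Manhattan campuses are both part of VANYHHS").
- **Outcome test.** SAP, Rationale for the study sample size, describes the power simulation: "For each iteration, we conducted two t-tests in accordance with the multiple testing corrections", and "we calculated power as the proportion of iterations in which both null hypotheses were rejected". No site term is mentioned.
- **Primary model.** The SAP section on interim analysis says "Besides the primary analyses described below, we will conduct exploratory mediation analyses", but no primary analysis follows.
- **Adjustment rules.** The same section lists baseline variables to compare: age, gender, race, education, then "comorbid medical conditions, and the Charlson comorbidity index and other potential co-variable measures". It continues: "We will assess whether any adjustments need to be made in the final statistical models if we determine the differences are clinically meaningful". The Definitions of Covariates section adds that baseline medical-record data may enter a multivariable analysis if the arms differ significantly. Neither section names site.

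**The concern.** Stratifying by site, if the allocation is restricted within site, removes between-site variation from the true sampling error of the arm difference. An analysis without site leaves that variation in the residual, so its estimated standard error is larger than the true one. The benefit of stratifying is then not collected: intervals are too wide, the test is conservative and some power is lost.

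The adjustment rules do not repair this. Both are triggered by an observed difference between arms, and the design works to keep the arms alike on site. The factor with the clearest claim to be in the model is therefore among the least likely to be picked up. Because no primary model is written out, the choice is also left until after the data are seen, although the stratum is known at randomisation.

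What is at stake is the precision of the preliminary effect-size estimate (Protocol, Study Goals, goal 3), with a minimum of 68 subjects.

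**Working it through.** **1. The plan's own figure.** The only sample-size figure with stated inputs is the 12-month yield, a recruitment funnel:

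- 1800 × (0.35 × 0.33 + 0.65 × 0.02) = 207.9 + 23.4 = 231.3 (stated 230)
- 230 × 0.70 = 161 (stated 160)
- 160 × 0.50 = 80; 80 × 0.95 = 76; 76 × 0.90 = 68.4 (stated 68)

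It reproduces, and it does not depend on the test or on site. The power simulation cannot be reproduced: the SAP states no alpha, effect size, SD or resulting power.

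**2. Size of the mismatch.** Assumptions, none from the documents: two equal sites, 1:1 allocation held within site, normal outcome with within-site SD 1, two-sided alpha of 5%. Let d be the difference in mean outcome between sites, in within-site SDs.

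- Between-site variance is d²/4, so site's share of outcome variance is R² = (d²/4)/(1 + d²/4).
- True SE of the arm difference: 2/√N. At N = 68 this is 2/√68 = 0.2425.
- SE that the t-test estimates: about 2√(1 + d²/4)/√N. The ratio is k = √(1 + d²/4).
- True type I error, normal approximation: 2[1 − Φ(1.96k)].
- Power for an assumed effect of 0.5 SD at N = 68: Φ(0.5/0.2425 − 1.96k) = Φ(2.062 − 1.96k). With site in the model k = 1, which gives 54.0%.

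| d | R² | k | Type I error, t-test | Power, t-test | Loss against 54.0% |
|---|---|---|---|---|---|
| 0 | 0 | 1.000 | 5.0% | 54.0% | 0 |
| 0.3 | 0.022 | 1.011 | 4.75% | 53.2% | 0.8 points |
| 0.5 | 0.059 | 1.031 | 4.34% | 51.6% | 2.4 points |
| 0.8 | 0.138 | 1.077 | 3.48% | 48.0% | 6.0 points |

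Simulation under the same assumptions (40,000 trials per setting) gives power of 52%, 51% and 47% with the t-test against about 53% with site, and type I error of 4.9%, 4.3% and 3.5%.

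**3. Dependence on the allocation scheme.** A second simulation (20,000 trials per setting, N = 68, effect set for about 80% power with site in the model) used assumed blocks of 4 within site:

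| R² | Estimated SE / true SE, t-test | Type I error, t-test | Power, t-test | Power with site |
|---|---|---|---|---|
| 0 | 0.99 | 5.3% | 78.6% | 78.6% |
| 0.02 | 1.01 | 4.7% | 78.4% | 79.0% |
| 0.05 | 1.02 | 4.4% | 77.4% | 78.9% |
| 0.10 | 1.05 | 4.0% | 75.4% | 78.8% |
| 0.20 | 1.11 | 2.9% | 71.3% | 79.1% |

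Type I error with site in the model stayed between 5.0% and 5.3%. Results at N = 120 and 150 are nearly the same, so a larger sample does not remove the mismatch.

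With separate unblocked lists per site the t-test's type I error stayed at about 5%. Site still gained power when it was prognostic: 77.7% against 68.4% at N = 68 and R² = 0.20.

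**4. Would the adjustment rules select site?** With blocks of 4, a chi-square test of site by arm was significant in 0 of 20,000 trials. With unblocked lists it was significant in about 4% to 6%. A significance trigger is therefore unlikely to bring site in under either scheme.

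**The case against.** A reader might infer that the trial will be analysed by plain t-test and that its standard errors are therefore wrong. The documents do not say so. The t-tests belong to the power simulation. For the trial itself the SAP speaks of primary analyses, final statistical models and a multivariable analysis without writing any of them out. What can be shown is that the model is missing and that site is not pre-specified in it. This part of the objection stands.

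A reader might also infer that the rules can never admit site. That is too strong. The comparison list is open-ended ("comorbid medical conditions, and the Charlson comorbidity index and other potential co-variable measures"), the trigger in the interim-analysis section is a clinical judgement, no blocking is stated, and dropout can disturb balance. Unlikely is the right word.

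The harm is also conditional and modest. It needs balance within site and a site effect, and the documents give no outcome difference between two campuses of one health system. The plan to report noise levels in the EDs promises no comparison by site and says nothing about outcomes. At 0.3 to 0.5 SD the standard error is only 1% to 3% too large, and the error is conservative. The phase is about feasibility, the SAP says its sample-size estimates matter only if continuation is approved, and revisits are only to be explored. All of this limits the importance of the point. It gives no reason to omit a factor known at randomisation, since including it loses essentially no power when site has no effect.

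**Conclusion.** The point holds as a gap in specification. Site stratifies the randomisation, appears in no described analysis, and is unlikely to enter through rules that wait for an observed imbalance.

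The numerical consequence assumes balanced allocation within two equal sites, a prognostic site and an unadjusted final comparison. Then the standard error is about 1%, 3% or 8% too large for site differences of 0.3, 0.5 or 0.8 SD, type I error is about 4.8%, 4.3% or 3.5%, and power at N = 68 falls by about 1 to 6 points. The site differences are an assumed range, and the upper end (about 14% of outcome variance) has no basis in the documents.

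If site is not prognostic there is no mismatch. Type I error is not inflated in any of these cases, and under the assumed balance site does not bias the estimate. This is a free improvement; it does not threaten the trial's validity.

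**What to change.** Write out the primary model and state that every between-arm comparison includes site as a fixed effect, whatever the observed balance:

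- scale outcomes: a linear model with arm and site;
- the exploratory three-day and 30-day revisits: a site-stratified comparison such as Mantel-Haenszel;
- missing data: site in any imputation model. The SAP imputes if loss exceeds 5% and elsewhere anticipates 10% attrition, so imputation may well be used;
- power: run the simulation with the same model.

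State the blocking scheme as well, because the size of the mismatch depends on it. The cost is a few sentences in the SAP and one degree of freedom.
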